5.2 EXCLUSION CRITERIA

Participants are excluded from the study if any of the following criteria apply:

- Disease duration of > 10 years from the onset of symptoms and an EDSS score at screening < 2.0
- Participants who are pregnant or breastfeeding, or intending to become pregnant during the study or within 28 days after the final dose of fenebrutinib

Women of childbearing potential must have a negative serum pregnancy test result at screening. If a urine pregnancy test is positive *at a subsequent visit*, it must be confirmed by a serum pregnancy test, ideally from the central laboratory.

- Men intending to father a child during the study or within 28 days after final dose of study drug
- A diagnosis of primary progressive MS or non-active secondary progressive MS
- Any known or suspected active infection at screening or baseline (excluding onychomycosis), or any major episode of infection requiring hospitalization or treatment with IV anti-microbials within 8 weeks prior to or during screening or treatment with oral anti-microbials within 2 weeks prior to or during screening
- History of progressive multifocal leukoencephalopathy (PML)
- History of cancer, including hematologic malignancy and solid tumors, within 10 years of screening

Basal or squamous cell carcinoma of the skin that has been excised and is considered cured and in situ carcinoma of the cervix treated with apparent success by curative therapy > 1 year prior to screening is not exclusionary

- Presence of other neurological disorders *that could interfere with the diagnosis of MS or with the assessments of efficacy or safety during the study*, including, but not limited to, the following:
 - History of ischemic cerebrovascular disorders (e.g., stroke, transient ischemic attack, spontaneous intracranial hemorrhage, or traumatic intracranial hemorrhage) or ischemia of the spinal cord
 - History or known presence of CNS or spinal cord tumor (e.g., meningioma, glioma)
 - History or known presence of potential metabolic causes of myelopathy (e.g., untreated vitamin B12 deficiency)
 - History or known presence of infectious causes of myelopathy (e.g., syphilis, Lyme disease, HTLV-1, herpes zoster myelopathy)
 - History of genetically inherited progressive CNS degenerative disorder (e.g., hereditary paraparesis, mitochondrial myopathy, encephalopathy, lactic acidosis, and stroke-like episodes [MELAS] syndrome)
 - Neuromyelitis optica spectrum disorder

- History or known presence of systemic autoimmune disorders potentially causing progressive neurological disease (e.g., lupus, anti-phospholipid antibody syndrome, Sjögren syndrome, Behçet disease)
- History or known presence of sarcoidosis
- History of severe, clinically significant brain or spinal cord trauma (e.g., cerebral contusion, spinal cord compression)
- Evidence of clinically significant psychiatric, pulmonary, renal, hepatic (including Gilbert syndrome), metabolic, gastrointestinal (GI), or cardiovascular disease (including arrhythmias or QTc prolongation), or endocrine disease (including uncontrolled diabetes, non-gallstone pancreatitis, or chronic pancreatitis) that, in the investigator's opinion, would preclude patient participation
- Presence of the New York Heart Association Class III and Class IV criteria for congestive heart failure
- Screening 12-lead ECG that demonstrates clinically relevant abnormalities that may affect patient safety or interpretation of study results, including QT interval corrected through use of Fridericia's formula (QTcF) >440 ms demonstrated by at least two ECGs >30 minutes apart
- Current treatment with medications that are well known to prolong the QT interval at doses that have a clinically meaningful effect on QT, as determined by the investigator
- History of ventricular dysrhythmias or risk factors for ventricular dysrhythmias, such as long QT syndrome and other genetic risk factors (e.g., Brugada syndrome); structural heart disease; coronary heart disease (symptomatic or with ischemia demonstrated by diagnostic testing, prior coronary artery bypass grafting, or coronary lesions > 70% diameter stenosis that have not been or cannot be revascularized); clinically significant electrolyte abnormalities (e.g., hypokalemia, hypomagnesemia, hypocalcemia); family history of sudden, unexplained death; or cardiac ion channel genetic mutations (e.g., congenital long QT syndrome)
- Participants undergoing dialysis or estimated glomerular filtration rate (eGFR) <60 mL/min/1.73 m² (may be repeated if eGFR 45–59 mL/min/1.73 m²)
- Any of the following laboratory results:
 - ALT or AST >2 × upper limit of normal (ULN)
 - Total bilirubin greater than 1.5 × ULN
 - Hemoglobin <9.5 g/dL (may be repeated if 9–9.4 g/dL)
 - White blood cell count <2000 cells/mm³ (μL)
 - Platelet count <100 × 10⁹/L (may be repeated if 80–100 × 10⁹/L)
 - Absolute neutrophil count ≤ 1500 cells/mm³ (μL)
 - IgG < 500 mg/dL

- Any concomitant disease that may require chronic treatment with systemic corticosteroids or immunosuppressants during the course of the 12-week double-blind study period
- History of alcohol or other drug abuse within 12 months prior to screening
- Positive screening tests for active, latent, or inadequately treated hepatitis B (as evidenced by either of the following):
 - Positive hepatitis B surface antigen (HBsAg)
 - Positive hepatitis B core antibody [total HBcAb] with detectable hepatitis B virus (HBV) DNA
- Positive screening tests for hepatitis C (positive hepatitis C antibodies)
- Evidence of active or latent or inadequately treated infection with tuberculosis (TB) as defined by the following:
 - A positive QuantiFERON® TB-Gold (QFT) test is found at screening. QFT testing should be performed through the central laboratory (see [Table A2-1](#) for test requirements).
 - An indeterminate QFT test should be repeated.
 - A positive QFT test or two successive indeterminate QFT results should be considered a positive diagnostic TB test.
 - An indeterminate QFT test followed by a negative QFT test should be considered a negative diagnostic TB test.
- Abnormalities in hepatic synthetic function tests (e.g., PT, INR, aPTT) judged by the investigator to be clinically significant
- History of hospitalization or transfusion for a GI bleed
- Known bleeding diathesis
- Any condition possibly affecting oral drug absorption
- History of or currently active primary or secondary (non-drug-related) immunodeficiency, including known history of HIV infection
- Inability to complete an MRI scan (contraindications for MRI scan, including but not restricted to, pacemaker, cochlear implants, intracranial vascular clips, surgery within 6 weeks of entry in the study, coronary stent implanted within 8 weeks prior to the time of the intended MRI scan) or contraindication to Gd administration
- Any previous history of organ transplantation
- Any previous treatment with bone marrow transplantation or hematopoietic stem cell transplantation
- Adrenocorticotrophic hormone or systemic corticosteroid therapy within 4 weeks prior to screening or during the screening period

Inhaled and topical corticosteroids are allowed

- Receiving an unstable dosing regimen of proton pump inhibitors (PPIs) or H₂receptor antagonist (H₂RAs) during the screening phase and/or no plan to remain at a stable dose for the duration of study treatment

Participants must not initiate PPIs or H₂RAs within 2 weeks prior to randomization.

- Treatment with IVIg or plasmapheresis within 12 weeks prior to randomization
- Sensitivity or intolerance to any ingredient (including excipients) of fenebrutinib
- Receipt of a live-attenuated vaccine within 6 weeks prior to randomization. Influenza vaccination is permitted if the inactivated vaccine formulation is administered.
- Need for systemic anticoagulation (oral or injectable) or anti-platelet agent other than nonsteroidal anti-inflammatory drugs, aspirin, and other salicylates (aspirin up to 162 mg QD is allowed)
- Previous treatment with fenebrutinib or another BTK inhibitor for any indication
- Treatment with strong CYP3A4 inhibitors, strong or moderate CYP3A4 inducers, within 7 days or 5 drug-elimination half-lives (whichever is longer) prior to randomization
- Treatment with CYP3A4 substrates with a narrow therapeutic window within 7 days or 5 drug-elimination half-lives (whichever is longer) prior to randomization
- Previous use of anti-CD20 therapies, unless the last infusion was more than 2 years prior to screening and B-cell count is normal at screening
- Previous use of fingolimod, siponimod, ozanimod, or ponesimod within 6 weeks of randomization
- Previous use of natalizumab within 6 months of randomization
- Previous treatment with azathioprine, mycophenolate mofetil, or methotrexate within 12 weeks of randomization
- Previous use of teriflunomide, unless teriflunomide plasma concentrations are <0.02 mg/L at screening
- Any previous treatment with cladribine, mitoxantrone, daclizumab, alemtuzumab, or cyclophosphamide
- Treatment with dimethyl fumarate or monomethyl fumarate within 4 weeks of randomization
- Treatment with any investigational agent within 5 half-lives of randomization
- Requirement for any prohibited concomitant medications
- Previous treatment with any other immunomodulatory or immunosuppressive medication not already listed above without appropriate washout as described in the applicable local label

If the washout requirements are not described in the applicable local label, then the wash out period must be 5 times the half-life of the medication. The PD

effects of the previous medication must also be considered when determining the required time for washout.

Note: No washout is required for interferon or glatiramer acetate.

Note: Participants screened for this study should not be withdrawn from therapies for the sole purpose of meeting eligibility for the trial. Participants who discontinue their current therapy for non-medical reasons should specifically be informed of their treatment options before deciding to enter the study.

5.3 LIFESTYLE CONSIDERATIONS

5.3.1 Meals and Dietary Restrictions

Use of the following foods is prohibited during the study and for at least 7 days prior to initiation of study treatment: furanocoumarin derivatives, such as those found in grapefruit, Seville oranges, pomegranates, or star fruit juice or products.

5.3.2 Caffeine, Alcohol, and Tobacco

This study has no caffeine, alcohol, or tobacco restrictions.

5.3.3 Activity

This study has no activity restrictions.

5.3.4 Contraception Requirements

During the study, participants must use contraception or take other precautions as described in Section 5.1.

5.4 SCREEN FAILURES

Individuals who do not meet the criteria for participation in this study (screen failure) may qualify for one re-screening opportunity (for a total of two screenings per individual) at the investigator's discretion. Individuals must re-sign the consent form prior to re-screening. The investigator will *maintain a record of* reasons for screen failure.

6. STUDY TREATMENT(S) AND CONCOMITANT THERAPY

Study treatment is defined as any investigational treatment, marketed product, placebo, or medical device intended to be administered to a study participant according to the study protocol.

The investigational medicinal product (IMP) for this study is fenebrutinib (*or fenebrutinib-matching placebo*). *Appendix 11 identifies all investigational medical products, and auxiliary medicinal products for this study.*

6.1 STUDY TREATMENTS ADMINISTERED

[Table 6](#) provides a description of assigned study treatments for this study.

Table 6 Study Treatment Description

Use	Fenebrutinib	Placebo
	Experimental	Placebo comparator
Type of medicinal product	IMP	IMP
Drug form	Tablet	Tablet
Unit Dose Strength(s)	100 mg	Not applicable
Dosage Level(s)	200 mg BID	2 tablets BID
Formulation(s)	Refer to pharmacy manual and Investigator's Brochure	Not applicable
Packaging	Pill bottle	Pill bottle
Labeling	Per local requirements	
Route of administration	Oral	Oral
Source	Sponsor	Sponsor

IMP = investigational medicinal product

6.1.1 **Fenebrutinib and Placebo**

Participants will take two 100 mg tablets PO BID for a total dose of 400 mg of fenebrutinib (or placebo) every day. Participants will self-administer two 100 mg tablets in the morning and two 100 mg tablets in the evening by mouth. The tablet should be swallowed whole with some water, can be taken with or without food, and should be taken at the same time each day. Participants should be instructed that a missed fenebrutinib (or matching placebo) dose should not be taken with the next scheduled dose. Administration of fenebrutinib (or matching placebo) should be staggered with antacid use (i.e., study drug should be taken 2 hours before or 2 hours after antacid administration). In addition, any antacids (e.g., bismuth subsalicylate, calcium carbonate, aluminum-magnesium hydroxide) should be recorded as concomitant medications.

All participants will provide PK samples on Day 1 (baseline), on Day 29 (DBT Week 4), and at other visits as specified in [Table 3](#). At the baseline and DBT Week 4 visits, the fenebrutinib (or matching placebo) morning dose will be administered at the morning (mandatory) clinic visit while the patient is fasting. The dates and times of the most recent prior meal, most recent antacid administration, last dose of oral study drug (prior to the clinic visit), and timing of oral study drug administration in the clinic should be recorded at each clinic visit with PK sampling.

6.2 PREPARATION, HANDLING, STORAGE, AND ACCOUNTABILITY

All IMPs required for completion of this study will be provided by the Sponsor. The study site (i.e., investigator or other authorized personnel e.g., pharmacist) is responsible for maintaining records of IMP delivery to the site, IMP inventory at the site, IMP use by each participant, and disposition or return of unused IMP, thus enabling reconciliation of all IMP received, and for ensuring that participants are provided with doses specified by the protocol.

The study site should follow all instructions included with each shipment of IMP. The study site will acknowledge receipt of IMPs supplied by the Sponsor using the interactive voice or web-based response system (IxRS) to confirm the shipment condition and content. Any damaged shipments will be replaced. The investigator or designee must confirm that appropriate temperature conditions have been maintained during transit, by temperature monitoring, for all IMPs received and that any discrepancies have been reported and resolved before use of the IMPs. All IMPs must be stored in a secure, environmentally controlled, and monitored (manual or automated) area in accordance with the labeled storage conditions, with access limited to the investigator and authorized staff.

Only participants enrolled in the study may receive IMPs, and only authorized staff may supply or administer IMPs.

The IMPs will either be disposed of at the study site according to the study site's institutional standard operating procedure or be returned to the Sponsor (if supplied by the Sponsor) with the appropriate documentation. The site's method of destroying Sponsor-supplied IMPs must be agreed to by the Sponsor. The site must obtain written authorization from the Sponsor before any Sponsor-supplied IMP is destroyed, and IMP destruction must be documented on the appropriate form.

Accurate records of all IMPs received at, dispensed from, returned to, and disposed of by the study site should be recorded on the drug accountability log.

Refer to the pharmacy manual and/or the fenebrutinib Investigator's Brochure for information on IMP preparation, storage, handling, and accountability.

6.3 TREATMENT ASSIGNMENT AND BLINDING

6.3.1 Treatment Assignment

This is a randomized, double-blind study. Randomization will be employed to minimize bias in treatment assignment and to provide the basis for valid statistical inference. After initial written informed consent has been obtained, all screening procedures and assessments have been completed, and eligibility has been established for a participant, the study site will obtain the participant's identification number and treatment assignment from an IxRS. Participants who discontinue treatment for any reason will not be

replaced, except for participants who withdraw before receiving any study treatment. Participants who enroll in this study and who have completed or prematurely discontinued from treatment as specified are not permitted to be re-randomized to this study under any circumstances.

Participants will be randomly assigned to one of two treatment arms: fenebrutinib or placebo. Randomization will occur in a 2:1 ratio through use of a permuted-block randomization method to ensure a balanced assignment to each treatment arm. Randomization will be stratified by presence or absence of T1 Gd+ lesions on the screening MRI.

6.3.2 Blinding

To maintain the integrity of the trial results and to prevent potential unblinding of the assigned arm as a result of adverse events or changes in laboratory results, the following additional measures will be implemented until the time of the primary analysis:

- Blinded, central MRI assessments: During the study, a blinded, central MRI reader will assess all MRI scans performed during the study. Of note, screening scans will be used for the assessment of patient eligibility and therefore will not be blinded. A local radiologist who is independent of the study team will review all scans at site for safety and report only significant nonMS-related findings to the treating investigator (or treating team).
- Blinding of laboratory parameters: Immunoglobulins (IgG, IgM, IgA, and total Ig) will be blinded until the primary database lock for the primary analysis.
- Study drug treatment allocation will remain blinded until the primary database lock for the primary analysis.

To facilitate analysis of the biological samples collected in this study, the treatment code will be released to the responsible analytical person when the samples have been received at the analytical site and are ready for assay. The result of the analysis must not be released with individual identification of the patient until after the unblinding for the primary analysis.

Study site personnel and participants will be blinded to treatment assignment until after the primary analysis. The Sponsor and its agents will also be blinded to treatment assignment, with the exception of individuals who require access to patient treatment assignments to fulfill their job roles during a study. These roles include the unblinding group responsible, clinical supply chain managers, sample handling staff, IxRS service provider, and iDMC members.

The PK samples must be collected from participants assigned to the comparator arm to maintain the blinding of treatment assignment; however, PK assay results for these participants are generally not needed for the safe conduct or proper interpretation of this study. Laboratories responsible for performing study drug PK assays will be unblinded to participants' treatment assignments to identify appropriate samples to be analyzed.

PK samples from participants assigned to the comparator arm will not be analyzed for study drug PK concentration except at baseline or by request (e.g., to evaluate a possible error in dosing).

If study treatment unblinding is necessary for a medical emergency (e.g., in the case of a serious adverse event for which participant management might be affected by knowledge of treatment assignment), the investigator will be able to break the treatment code by contacting the IxRS. The treatment code should not be broken except in emergency situations. The investigator is not required to contact the Medical Monitor prior to breaking the treatment code. However, the investigator should *inform* the Medical Monitor *that* the treatment code has been broken.

If the investigator wishes to know the identity of the study drug for any reason other than a medical emergency, he or she should contact the Medical Monitor directly prior to unblinding.

The investigator should document and provide an explanation for any non-emergency unblinding. If the Medical Monitor agrees to participant unblinding, the investigator will be able to break the treatment code by contacting the IxRS.

As per health authority reporting requirements, the Sponsor's Drug Safety representative will break the treatment code for all serious, unexpected suspected adverse reactions that are considered by the investigator or Sponsor to be related to an *a drug listed in Section 8.3.4*. The participant may continue to receive treatment, and the investigator, participant, and Sponsor personnel, with the exception of the Drug Safety representative and personnel who must have access to participant treatment assignments to fulfill their roles (as defined above), will remain blinded to treatment assignment.

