4.2.8 Rationale for the Optional Cerebrospinal Fluid Substudy

Fenebrutinib reduces both B-cell and myeloid lineage-cell activation by binding to and blocking the function of BTK; effects on both these cell types may be important to the drug's effect on participants with MS. Persistent blood-brain barrier disruption and leakage have been reported in participants with MS. It may be important to estimate fenebrutinib's CNS exposure level in participants with MS in order to understand the drug's potential to affect CNS compartmentalized inflammation. Clinically, CSF drug levels have frequently been used to estimate drug exposure in the CNS. The optional CSF substudy proposes to collect CSF from approximately 10 participants at two timepoints. The fenebrutinib concentration may be measured in the CSF and compared to the serum concentration measured contemporaneously. To evaluate fenebrutinib's effect on antibody formation within the CNS, the CSF to serum IgG index may be measured, as will the number of unique CSF oligoclonal bands.

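### Protocol 6.3.2 releases the treatment code before assay for all biological samples, although only the fenebrutinib concentration assays have a stated need for it

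*Protocol*

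**What the plan says.** Protocol 6.3.2 contains two separate provisions that unblind laboratory staff.

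- **General provision.** For the study's samples as a whole, with no limit to PK, "the treatment code will be released to the responsible analytical person"; this release takes place "when the samples have been received at the analytical site and are ready for assay". The next sentence adds a safeguard: "The result of the analysis must not be released with individual identification of the patient until after the unblinding for the primary analysis".
- **PK provision.** "Laboratories responsible for performing study drug PK assays will be unblinded to participants' treatment assignments to identify appropriate samples to be analyzed". The reason follows: comparator-arm samples "will not be analyzed for study drug PK concentration except at baseline or by request".

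The same section says that treatment allocation stays blinded until the database lock for the primary analysis. It exempts sponsor staff and agents whose jobs require the code and gives a list of roles. The list includes sample handling staff but does not name biomarker or CSF analysts.

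SAP 1.2.1 repeats the PK provision and does not carry the general one.

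**The concern.** The general provision has no limit to drug assays. Read literally, the people running NfL, flow cytometry and the CSF inflammatory assays receive the treatment code before they produce a result.

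Several of these measures are meant to show fenebrutinib activity against placebo. Protocol 4.2.5 plans to compare NfL with placebo-treated participants, and SAP 5.5.1.3 to 5.5.1.6 allow placebo-adjusted estimates for a range of markers. Protocol 4.2.8 says the CSF IgG index may be measured, "as will the number of unique CSF oligoclonal bands". Where a result depends partly on judgement, an analyst who knows the arm can shift it without intending to. A reader of the eventual biomarker report would have no assurance in the protocol that this was prevented.

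**Working it through.** No figure is stated and no arithmetic decides the point. The check is a comparison of the texts.

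1. **Scope and timing.** The general provision in Protocol 6.3.2 refers to the study's biological samples as a whole. The code is released when samples are ready for assay, so before results exist.

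2. **Can it be read as PK only?** Not without making the later PK paragraph redundant. That paragraph already unblinds the PK laboratories and gives its own reason.

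3. **Does the PK reason carry over?** The PK laboratories need the code to choose samples, because most comparator-arm samples are not assayed. Protocol 9.3 and SAP 4 analyse biomarker endpoints on all randomized patients by assigned arm. Samples from both arms must therefore be assayed, and there is no selection by arm to make. No other reason specific to non-PK assays is given.

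4. **Which CSF assays are affected?** Protocol Table 8 lists both PK and biomarker samples in CSF at Week 12. CSF fenebrutinib concentration is a drug assay, so the code has the same use there as in plasma. The point applies to CSF IgG index, oligoclonal bands and CSF NfL.

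5. **Consistency.** The general provision does not fit the statement that allocation stays blinded until the primary database lock, the list of unblinded roles, or SAP 1.2.1. Protocol 8.7 also allows biomarker samples to go to the sponsor or a designee, so the provision could reach sponsor staff whom 6.3.2 otherwise keeps blinded.

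6. **What the safeguard does.** It restricts who sees identified results before unblinding. It does not restrict what the analyst knows when generating them.

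7. **Which endpoints are exposed?**
   - NfL, CCL4, CXCL13 and the IgG and albumin indices (SAP 5.5.1.3 to 5.5.1.5) are numeric measurements. The documents show no particular susceptibility to reader judgement.
   - Oligoclonal bands (Protocol 4.2.8, SAP 5.5.1.3) and the lymphocyte subsets from flow cytometry (SAP 5.5.1.6) are the more exposed ones. This assumes that band reading and cell gating involve judgement; the documents do not describe either procedure.
   - All are exploratory. SAP 5.5 says such analyses may be performed as data allow and may be reported separately.

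8. **Scale in CSF.** The substudy is optional and aims for about 10 participants (Protocol 4.2.8). If they follow the 2:1 allocation, 10 × 1/3 ≈ 3 are on placebo.

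9. **MRI endpoints.** Protocol 8.1.1 and SAP 5.3.1 have the scans read centrally by a centre blinded to treatment. The sample code does not touch them.

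**The case against.** The strongest reply is that the general sentence is loose drafting and that the PK paragraph shows how it is carried out. Allocation is said to stay blinded, the named unblinded roles include no biomarker analyst, and the only laboratories expressly unblinded are those doing drug assays. Laboratory handling is left to a manual that is not among these documents. This shows that the biomarker analysts may never receive the code. It does not make the text safe: the general sentence remains a stated rule, the role list is introduced as non-exhaustive, and the SAP by its own introduction supersedes analysis details, not laboratory procedure.

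A second reply is that disclosure is already contained. Identified results are withheld until unblinding, 6.3.2 keeps immunoglobulin results blinded until the primary lock, and Appendix 2 withholds potentially unblinding laboratory results from sites and blinded personnel. That stands as an answer to wider leakage, but none of it expressly blinds the analyst.

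A third reply concerns importance. Oligoclonal band status is only summarized descriptively in SAP 5.5.1.3, and with about 3 placebo participants a CSF comparison carries little weight, blinded or not. That stands, and it limits the size of the point.

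A reader might also infer that the release serves no purpose at all. The documents do not support that. The protocol gives a general purpose, to facilitate analysis; what is absent is a reason specific to the non-PK assays.

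**Conclusion.** The point holds as a wording fault with limited consequences. Protocol 6.3.2 releases the code before assay for all biological samples, while only fenebrutinib concentration in plasma and CSF has a stated need for it. The rule is at odds with the rest of 6.3.2 and with SAP 1.2.1.

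Any resulting bias is confined to exploratory biomarker and CSF endpoints, mainly those involving reader judgement. Neither its size nor its direction can be computed from the documents. The conclusion assumes that the general sentence is applied as written.

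Two stronger readings should be avoided. One is that every between-arm biomarker comparison in SAP 5.5.1.3 to 5.5.1.6 is affected; this is not shown, since most of the measures are numeric and band status has no between-arm model. The other is that the trial's main result is compromised; the MRI primary and secondary endpoints are read blinded and are unaffected.

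**What to change.** In Protocol 6.3.2, limit the code release to personnel performing fenebrutinib concentration assays in plasma and CSF. State that all other biomarker, flow cytometry and CSF inflammatory assays are run blinded to treatment until the primary database lock. Align the list of unblinded roles with this. SAP 1.2.1 already names only the PK laboratories and would then agree.

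The cost is a few lines of text. No sample, visit, sample size or analysis changes, and no non-PK assay described in the documents has a stated need for the code. If arm-balanced assay batches are wanted, the sample handling staff already on the unblinded list could arrange them without the analyst knowing the arm.
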